7.3 Exploratory efficacy outcomes

The following measures will be collected and analyzed as exploratory efficacy outcomes.

7.3.1 Nasal Obstruction Symptom Evaluation

The NOSE scale is a validated PRO instrument that allows participants to quantify their perception of nasal obstruction.⁴ The tool measures the severity of 5 symptoms (nasal congestion

or stuffiness, nasal blockage or obstruction, trouble breathing through the nose, trouble sleeping, and difficulty breathing through the nose during exercise or exertion) on a Likert scale from 0 (no problem) to 4 (severe problem). The sum of the 5 symptom scores is multiplied by 5 to give a score range from 0 to 100.

Lipan and Most developed a clinically relevant classification system for NOSE scores: mild (5-25 points), moderate (30-50 points), severe (55-75 points), or extreme (80-100 points).⁵ This system has been used to define treatment responders. In previous clinical studies, responders were defined as participants who had at least 1 NOSE class improvement or a NOSE score reduction of at least 20% from baseline.

The mean \pm SD for the change from baseline to the 30-day and 90-day follow-ups in the total NOSE score will be calculated for matched pairs. Significance of the change from baseline will be assessed using a paired *t*-test with (2-sided) 0.05 alpha level indicating significance. If the data are not normally distributed, a Wilcoxon signed rank test will be conducted in place of the *t*-test and the median and interquartile range will be presented instead of the mean \pm SD. Normality will be assessed by the Shapiro-Wilk test, where a *p*-value <0.05 indicates the non-normality of the data.

The count and percentage of participants who meet the NOSE responder definition will be calculated using the previously used definition of NOSE responder (see above). Individual NOSE symptom scores may also be analyzed.

7.3.2 Sino-Nasal Outcomes Test (SNOT-22)

The SNOT-22 is a validated PRO consisting of 22 items, each item is scored using a 5-point Likert scale from 0 (no problem) to 5 (problem as bad as it can be) and is assessed over the previous 2-week period. The total SNOT-22 score is the sum of the responses, producing a total possible score from 0 to 110, with higher scores indicating worse symptoms. The minimal clinically important difference (MCID) for the total SNOT-22 is -8.9 points.⁶

The mean \pm SD for the change from baseline to the 30-day and 90-day follow-ups in the total SNOT-22 score will be calculated for matched pairs. Significance of the change from baseline will be assessed using a paired *t*-test with (2-sided) 0.05 alpha level indicating significance. If the data are not normally distributed, a Wilcoxon signed rank test will be conducted in place of the *t*-test and the median and interquartile range will be presented instead of the mean \pm SD. Normality will be assessed by the Shapiro-Wilk test, where a *p*-value <0.05 indicates the non-normality of the data. Additionally, the count and percentage of participants who achieve the MCID (≥ 8.9 points) will be calculated.

7.3.3 Nasal symptom visual analog scale (VAS)

A 100-mm VAS is used to evaluate the symptoms rhinorrhea (runny nose), nasal congestion (stuffiness), and overall nasal symptoms. A response of 0-mm (left side) indicates no symptoms and a response of 100-mm (right side) indicates severe symptoms. At baseline and at the 30-day

and 90-day visits, participants marked on the continuum where they ranked their symptoms over the preceding week.

The mean \pm SD for the change from baseline to the 30-day and 90-day follow-ups in the individual symptom VAS score and the overall VAS score will be calculated for matched pairs. Significance of the change from baseline will be assessed using a paired *t*-test with (2-sided) 0.05 alpha level indicating significance. If the data are not normally distributed, a Wilcoxon signed rank test will be conducted in place of the *t*-test and the median and interquartile range will be presented instead of the mean \pm SD. Normality will be assessed by the Shapiro-Wilk test, where a *p*-value <0.05 indicates the non-normality of the data.

7.3.4 Mini Rhinoconjunctivitis Quality of Life Questionnaire – (mini RQLQ)

The mini RQLQ is a validated PRO that measures functional impairments due to allergic or non-allergic rhinoconjunctivitis.⁷ The assessment consists of 14 questions related to 5 domains of rhinoconjunctivitis: nasal symptoms, eye symptoms, other symptoms, practical problems, and activities. Each of the 14 items is scored from 0 (no impairment) to 6 (severely impaired). An overall score is calculated from the mean of the 14 item responses. Domain scores are the mean of the item scores within that domain. The MCID for the mini RQLQ has been established as 0.7.⁸

The mean change from baseline will be assessed for the mini RQLQ at the 30-day and 90-day follow-ups. The significance of the change will be assessed using a paired *t*-test with a (2-sided) 0.05 alpha level indicating significance. If the data are not normally distributed, a Wilcoxon signed rank test will be conducted in place of the *t*-test and the median and interquartile range will be presented instead of the mean \pm SD. Normality will be assessed by the Shapiro-Wilk test, where a *p*-value <0.05 indicates the non-normality of the data. The count and percentage of participants achieving the MCID will be calculated on the total mini RQLQ score.

7.3.5 Clinician Global Impression of Improvement – (CGI-I)

The Clinical Global Impression--Improvement (CGI-I) is a clinician-completed assessment evaluating the clinician's impression of a patient's response to treatment based on their clinical experience.⁹ The CGI-I is a 7-point Likert scale that ranges from 1 (very much improved) to 7 (very much worse). The CGI-I is completed by the physicians at the 30-day and 90-day follow-up visits to evaluate the physicians' impression of participant improvement over baseline.

The count and percentage of participants in each category will be calculated at the 30-day and 90-day follow-up visits. In addition, the count and percent of participants experiencing any improvement (very much improved, much improved, and minimally improved) at each visit will be calculated.

8 Safety Outcomes

8.1 Safety analysis cohort

Safety analysis cohort is all participants treated with the ClariFix device.

8.2 Safety outcomes

All AEs (serious and nonserious) will be adjudicated by the Medical Monitor for the following:

- AE term
- Relatedness (to study device and procedure)

The relatedness will be initially determined by the investigator; however, if there is a discrepancy between the investigator and the Medical Monitor, the final analysis will be based on the adjudication determination. Adjudication findings will be entered into the Medrio EDC.

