### 8.4.3 DEFINITION OF SERIOUS ADVERSE EVENTS (SAE)

An adverse event (AE) or suspected adverse reaction is considered "serious" if, in the view of either the investigator or sponsor, it results in any of the following outcomes: death, a life-threatening adverse event, inpatient hospitalization or prolongation of existing hospitalization, a persistent or significant incapacity or substantial disruption of the ability to conduct normal life functions, or a congenital anomaly/birth defect. Important medical events that may not result in death, be life-threatening, or require hospitalization may be considered serious when, based upon appropriate medical judgment, they may jeopardize the participant and may require medical or surgical intervention to prevent one of the outcomes listed in this definition.

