#### 8.4.5.2 RELATIONSHIP TO STUDY INTERVENTION

All adverse events (AEs) must have their relationship to both the study device and study procedure assessed by the clinician who examines and evaluates the subject based on temporal relationship and his/her clinical judgment. The degree of certainty about causality will be graded using the categories below. In a clinical trial, the study product must always be suspect.

- **Definitely Related** – There is clear evidence to suggest a causal relationship to either the study device or the study procedure, and other possible contributing factors can be ruled out. The clinical event, including an abnormal laboratory test result, occurs in a plausible time relationship to study device or the study procedure and cannot be explained by concurrent disease or other drugs or chemicals. The event must be phenomenologically definitive.
- **Probably Related** – There is evidence to suggest a causal relationship to either the study device or the study procedure, and the influence of other factors is unlikely. The clinical event, including an abnormal laboratory test result, occurs within a reasonable time after administration of the study intervention, is unlikely to be attributed to concurrent disease or other drugs or chemicals.
- **Potentially Related** – There is some evidence to suggest a causal relationship to either the study device or the study procedure (e.g., the event occurred within a reasonable time after study procedure). However, other factors may have contributed to the event (e.g., the participant’s clinical condition, other concomitant events).
- **Unlikely to be related** – A clinical event, including an abnormal laboratory test result, whose temporal relationship to either the study device or the study procedure makes a causal relationship improbable (e.g., the event did not occur within a reasonable time after study procedure) and in which other drugs or chemicals or underlying disease provides plausible explanations (e.g., the participant’s clinical condition, other concomitant treatments).
- **Not Related** – The AE is completely independent of either the study device or the study procedure, and/or evidence exists that the event is definitely related to another etiology. There must be an alternative, definitive etiology documented by the clinician.

---

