3.1.1 Study Endpoints

The primary endpoint is the incidence of procedure-related serious adverse events (SAEs) and/or serious adverse device effects (SADEs)

Secondary endpoints are:

- Incidence of procedure-related adverse events (AEs) and/or adverse device effects (ADEs)
- Tolerability of treatment as rated by participant verbal report of pain/discomfort on the 11-point Numeric Pain Rating Scale (NPRS)
- Change from baseline in nasal symptoms using the reflective Total Nasal Symptom Score (rTNSS) at 30 and 90 days post treatment
- Change from baseline in nasal congestion and turbinate hypertrophy as assessed by nasal endoscopy 30 and 90 days post treatment

Additional exploratory analyses are:

- Procedural characteristics
- Physician evaluation of ease of treatment delivery using study device for inferior meatus location
- Change from baseline in patient-reported outcome (PRO) assessments at 30 and 90 days post treatment:
 - Nasal Obstruction Symptom Evaluation (NOSE)
 - Sino-Nasal Outcomes Test (SNOT-22)
 - Nasal symptom visual analog scale (VAS)
 - Mini Rhinoconjunctivitis Quality of Life Questionnaire (mini RQLQ)

- Physician assessment of participant change from baseline as measured by the Clinical Global Impressions – Improvement

All statistical analyses will be performed using SAS (version 9.4), unless otherwise noted.

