8.2.1 Serious adverse events

The primary safety endpoint is the number of participants with 1 or more SAEs and/or SADEs. SADEs are SAEs that are adjudicated to be related (possibly, probably, or definitely) to the ClariFix device and/or procedure. The total number of SAEs will also be presented.

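### The Medical Monitor's relatedness call replaces the investigator's in the final safety analysis, and no planned summary shows the investigator-assessed result beside it.

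*SAP*

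**What the plan says.** Protocol 8.4.5.2 requires the relationship of each AE to device and procedure to be "assessed by the clinician who examines and evaluates the subject based on temporal relationship and his/her clinical judgment". Protocol 9.4.4 tabulates related events without saying whose grading is used. The Protocol text available for review describes no adjudication step.

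SAP 8.2 adds one: "All AEs (serious and nonserious) will be adjudicated by the Medical Monitor for the following", the two items being the event term and relatedness to device and procedure. The investigator grades relatedness first, but "if there is a discrepancy between the investigator and the Medical Monitor, the final analysis will be based on the adjudication determination". The adjudicated finding is entered in the EDC.

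The derived categories follow the adjudicated call. SAP 8.2.1 states that "SADEs are SAEs that are adjudicated to be related (possibly, probably, or definitely) to the ClariFix device and/or procedure", and SAP 8.2.2 defines ADEs in the same way. Two outputs for serious events do not depend on relatedness: SAP 8.2.1 adds that "The total number of SAEs will also be presented", and SAP 8.2.2 provides a by-participant listing of SAEs, SADEs and ADEs. The columns of that listing are not given. SAP 10.4 plans no sensitivity analysis.

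The primary endpoint is worded in two ways. SAP 3.1.1, in line with the Protocol synopsis and Protocol section 3, ties it to relatedness: "The primary endpoint is the incidence of procedure-related serious adverse events (SAEs) and/or serious adverse device effects (SADEs"). SAP 8.2.1 does not: "The primary safety endpoint is the number of participants with 1 or more SAEs and/or SADEs". The secondary AE endpoint is split in the same way between SAP 3.1.1 and SAP 8.2.2.

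**The concern.** This is an open-label, single-arm study whose primary result will be a very small count. Under the SAP 3.1.1 and Protocol definition, relatedness decides whether an SAE is in that count. When the two assessors disagree, only the adjudicated grading is carried into the analysis. A reader of the planned summaries would see zero related SAEs, or one, without knowing that the physician who examined the participant had graded the event the other way.

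At stake is the transparency of the main safety result. One reclassification can decide whether that result is zero, and the plan gives no summary from which the reclassification could be recognised.

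**Working it through.** The plan states no figure to reproduce. The sample of 30 is a convenience sample, and SAP 3.1.2 gives no hypothesis or power for the primary endpoint. The check has two parts: where a reclassified event goes, and how far one such event moves the result.

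**Where a reclassified event goes**

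| Investigator → adjudicated | Endpoint per SAP 3.1.1 | Endpoint per SAP 8.2.1 / 8.2.2 | SADE or ADE count | All-SAE or all-AE count | SAP 8.2.2 listing |
|---|---|---|---|---|---|
| SAE: related → unrelated | leaves | stays | leaves | stays | stays |
| SAE: unrelated → related | enters | already in | enters | unchanged | already in |
| Nonserious AE: related → unrelated | leaves | stays | leaves | stays | leaves |
| Nonserious AE: unrelated → related | enters | already in | enters | unchanged | enters |

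Three things follow.

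- The rule works in both directions.
- A downgraded SAE is never lost from sight as an event. What may be lost is the fact that the investigator graded it related.
- The third row is the weakest point. A nonserious AE adjudicated to unrelated leaves both the ADE count and the listing, and survives only within the counts of all AEs. Protocol 9.4.6 does not close this gap, because it makes AE listings optional.

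**Size of one reclassified SAE (SAP 3.1.1 definition)**

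Input: n = 30 treated (SAP 3.1.3). Exact Clopper-Pearson 95% limits:

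- x = 0: upper = 1 − 0.025^(1/30) = 0.116. Result: 0/30, 0% to 11.6%.
- x = 1: lower = 1 − 0.975^(1/30) = 0.0008; upper = 97.5th centile of Beta(2, 29) = 0.172. Result: 1/30 = 3.3%, 0.1% to 17.2%.

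One reclassified participant therefore moves the point estimate by 1/30 = 3.3 percentage points and the upper limit by 17.2 − 11.6 = 5.6 points. Neither document plans an interval for this endpoint; these are used here only to show scale.

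**Is a single related SAE plausible?**

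Protocol 2.3 reports, for the earlier 100-subject study, two SAEs, one of them graded possibly device related. That study treated the middle meatus only, so its 1/100 is an assumption here and a range is needed. The chance of at least one affected participant in 30 is 1 − (1 − p)^30:

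| Assumed true rate p | Chance of at least one |
|---|---|
| 0.5% | 14% |
| 1% | 26% |
| 2% | 45% |
| 5% | 79% |

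These are chances that a related SAE occurs at all. The documents give no basis for the chance that the two assessors would then disagree.

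**The case against.** The strongest defence is that one prespecified, prevailing adjudication of every AE is an accepted way to obtain consistent grading across sites. It can add events as well as remove them, the investigator in an open-label study is not blinded either, and the documents give no reason to expect mainly downgrades. That stands: the override itself is not an error.

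It is also fair to say that no decision hangs on the count. The primary endpoint has no hypothesis, and SAP 10.1 sets no termination criteria. That limits the consequence but does not remove the reporting gap.

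A reader might infer more than the documents support:

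- *A downgraded SAE disappears from the results.* It does not. It remains in the SAE total and the by-participant listing, and on the SAP 8.2.1 wording it remains in the primary count too. Since the listing's columns are not specified, it cannot be said that the investigator's grading will be absent there, only that nothing requires it.
- *The SAP contradicts the Protocol.* Protocol 8.4.5.2 says who grades causality at the site, and the SAP keeps that step. Neither that section nor Protocol 9.4.4 says whose grading governs the analysis. The SAP adds a step; it does not break a stated rule.
- *Relatedness must follow the same rule as seriousness.* Protocol 8.4.3 calls an event serious when it is so "in the view of either the investigator or sponsor". That wording concerns seriousness only. Counting an event as related if either assessor says so is a conservative option, not something the Protocol requires.
- *Seriousness also needs adjudication.* The same clause already lets a sponsor-side view make an event serious.
- *The Medical Monitor is not independent.* Front matter, including contact pages, was removed from the documents reviewed, so silence on this cannot be held against the plan.

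**Conclusion.** The point holds as a gap in reporting, together with an unreconciled endpoint definition. The adjudicated call governs the final analysis, SADEs and ADEs depend on it alone, and no planned summary gives the investigator-assessed result.

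The shift from 1/30 to 0/30 from one downgrade rests on two assumptions: that 30 participants are treated, and that the primary endpoint is the relatedness-limited one in SAP 3.1.1 and the Protocol. If SAP 8.2.1 is taken as written, the primary count does not move and only the SADE label changes. That the effect on the primary result depends on which SAP section is followed is itself a reason to reconcile them.

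For nonserious AEs the gap does not depend on that choice: on either wording, a downgraded event leaves the ADE count and the listing. The change is worth making because both gradings will already exist and this is the study's main safety result. It does not justify replacing the adjudication rule.

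**What to change.** In the SAP:

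1. Keep the adjudicated relatedness call as the main analysis.
2. Reconcile SAP 8.2.1 with SAP 3.1.1 so that there is one primary endpoint definition, and align SAP 8.2.2 in the same way for the secondary AE endpoint.
3. Tabulate participants with related SAEs, and with related AEs, by the investigator's call beside the adjudicated call. State how the Protocol 8.4.5.2 grade *potentially related* maps to the SAP's *possibly*, so that the two columns use the same cut.
4. Specify that the listing shows both calls, and extend it to every event on which they differ, serious or not.

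The cost is SAP wording, one extra table and a wider listing. Both gradings are already made and the adjudication is already entered in the EDC, so no new data are needed. The downside for the sponsor is that the investigator-assessed rate may read less favourably than the adjudicated one.

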8.2.1 Serious adverse events

The primary safety endpoint is the number of participants with 1 or more SAEs and/or SADEs. SADEs are SAEs that are adjudicated to be related (possibly, probably, or definitely) to the ClariFix device and/or procedure. The total number of SAEs will also be presented.

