## 1 PROTOCOL SUMMARY

### 1.1 SYNOPSIS

Title:	Feasibility Study of Multi-Treatment Posterior Nasal Nerve Modulation for Treatment of Chronic Rhinitis
Study Description:	Prospective, non-randomized, feasibility study of adult patients for treatment to the posterior nasal nerve using cryotherapy at multiple treatment sites within the nasal cavity.
Objectives:	
Evaluate the feasibility of treatment to the posterior nasal nerve at both the middle and inferior meatus locations within the nasal cavity.
 
Primary Objective: Evaluate the safety of treatment to the inferior meatus location
 
Secondary Objectives: Evaluate the effectiveness and tolerability of treatment at the inferior meatus location

Endpoints:	
Primary Endpoint: Incidence of procedure related Serious Adverse Events (SAEs) and/or Serious Adverse Device Effects (SADE)
 
Secondary Endpoints:
 
 
• Incidence of procedure-related Adverse Events (AEs) or Adverse Device Effects (ADEs).
 
• Tolerability of treatment via verbal report of pain/discomfort.
 
• Nasal symptoms using rTNSS scale at 30- and 90-Days post-treatment.
 
• Nasal congestion and turbinate hypertrophy as assessed by physician at 30- and 90-Days post-treatment.
 
 
Exploratory Endpoints:
 
 
• Physician Evaluation of ease of treatment delivery using study device for inferior meatus location.
 

Study Population:	Up to 30 adult subjects diagnosed by ENT Physician with chronic rhinitis will be enrolled and treated in-office.
Clinical Site(s)	Up to 5 U.S. sites
Study Device:	Arrinex ClariFix™ Cryotherapy Device
Study Duration:	9 Months
Participant Duration:	Approximately 3.5 months

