## 8.4 ADVERSE EVENTS, ADVERSE DEVICE EFFECTS, SERIOUS ADVERSE EVENTS AND UNEXPECTED ADVERSE DEVICE EFFECTS

In this study, the following types of adverse events will be collected and documented:

- ClariFix Device-related Adverse Device Effects (ADE)
- Cryotherapy procedure-related Adverse Events (AE)
- Head, ear, nose, throat, and breathing/lung related AEs, including anticipated AEs
- All Serious Adverse Events (SAE)
- Unanticipated Adverse Device Effects (UADE)

Anticipated adverse events are identified in the ClariFix IFU (See Appendix I).

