#### 9.4.4 SAFETY ANALYSES

The overall incidence (i.e., number and percent of subjects with 1 or more adverse event) of adverse events, serious adverse device events, serious adverse events, and device and/or procedure related events (e.g., possibly, probably or definitely related) will be calculated from time of treatment through the entire duration of follow-up. The overall incidence of mild, moderate and severe events will be calculated by considering the most severe event for each subject.

In addition, the overall incidence for each adverse event type will be calculated. The adverse event types will be classified as defined in Section 8.4.

---

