8.2.2 All device-related/procedure-related adverse events

The secondary safety endpoint is the number of participants with 1 or more AE and/or ADE. ADEs are AEs that are adjudicated to be related (possibly, probably, or definitely) to the ClariFix device and/or procedure. The total number of AEs and ADEs will also be presented.

A listing by participant of all SAEs, SADEs, and ADEs will be provided.

9 Protocol Deviations

Protocol deviations will be summarized by deviation type, and overall using counts and percentages. A listing of all protocol deviations by participant will also be provided.

10 Additional Statistical Analyses

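### SAP 8.2.1 omits the procedure-related limit from the primary endpoint, so its counting rule takes in every SAE and conflicts with SAP 3.1.1 and Protocol 1.1 and 3

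*SAP*

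**What the plan says.** Where the endpoints are defined, the limit is present. Protocol 1.1 gives the primary endpoint as "Incidence of procedure related Serious Adverse Events (SAEs) and/or Serious Adverse Device Effects (SADE", and the table in Protocol 3 repeats it. SAP 3.1.1 agrees: "The primary endpoint is the incidence of procedure-related serious adverse events (SAEs) and/or serious adverse device effects (SADEs".

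The analysis section, SAP 8.2.1, states the count without the limit: "The primary safety endpoint is the number of participants with 1 or more SAEs and/or SADEs". Its next sentence defines the second term: "SADEs are SAEs that are adjudicated to be related (possibly, probably, or definitely) to the ClariFix device and/or procedure". It adds that the total number of SAEs will be shown.

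Three other places bear on the point:

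- Protocol 8.4 lists among the events to be collected "All Serious Adverse Events (SAE", with no relatedness condition.
- SAP 8.2 has the Medical Monitor adjudicate the relatedness of every AE. Where that differs from the investigator's view, "the final analysis will be based on the adjudication determination".
- SAP 8.2.2 uses the same short form for the secondary endpoint: "The secondary safety endpoint is the number of participants with 1 or more AE and/or ADE". Its heading, however, does mention device and procedure relatedness.

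**The concern.** The endpoint definition and the counting rule give different results whenever a participant has an SAE unrelated to device and procedure. The SAP sets no order of precedence between 3.1.1 and 8.2.1. The study is open-label, so the choice could be made after the SAEs are known.

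An all-cause count also includes events that say nothing about the treatment, whereas the primary objective is the safety of treating the inferior meatus. Under the literal rule, the relatedness adjudication in SAP 8.2 has no influence on the primary result.

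**Working it through.** **Set logic.** The documents state no derived figure for this endpoint, so there is nothing to reproduce; the check starts from the definitions.

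- Let S be the participants with at least one SAE, and R those with at least one SAE adjudicated as related to the device and/or procedure.
- By the SADE definition in SAP 8.2.1, R is the set with at least one SADE, and R is contained in S.
- The rule in SAP 8.2.1 counts S ∪ R = S, that is, any SAE. The SADE term adds nothing.
- The definition in SAP 3.1.1 counts participants with a procedure-related SAE or a SADE. Both groups lie in R, and SADEs alone make up R, so the count is R.
- The two counts differ by the participants in S but not in R: those whose only SAEs are unrelated. Protocol 8.4 ensures that such events are recorded.

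**Effect of one such participant.** Take N = 30 (SAP 3.1.3), one participant with an unrelated SAE and none with a related one.

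| Rule | Result | Exact 95% CI |
|---|---|---|
| SAP 8.2.1 as written | 1/30 = 3.3% | 0.1% to 17.2% |
| SAP 3.1.1 and Protocol 1.1 and 3 | 0/30 = 0% | 0% to 11.6% |

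**How likely a difference is (illustration).** The only figure in the documents comes from the 100-subject post-market study in Protocol 2.3, which treated the middle meatus only. It reported two SAEs through 90 days, one not related and one possibly device related. The all-cause rule would have counted two SAEs there and the related-only rule one. One unrelated event is one subject, so the rate is 1/100 = 1%, with an exact 95% CI of 0.03% to 5.4%.

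For a per-participant rate p of unrelated SAEs, P(at least one in 30) = 1 − (1 − p)^30:

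| p | Chance of at least one in 30 |
|---|---|
| 0.025% (lower CI limit) | 0.8% |
| 0.5% (assumed) | 14.0% |
| 1% (1/100) | 26.0% |
| 2% (assumed) | 45.5% |
| 5.4% (upper CI limit) | 81% |

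The two rules differ in that event unless each such participant also has a related SAE.

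No similar figure can be given for SAP 8.2.2, because the documents give no participant-level AE counts.

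**The case against.** The strongest reply is that SAP 8.2.1 is shorthand. The limit appears in all three places where the endpoint is defined. Relatedness is adjudicated for every AE, and defining SADEs straight after the rule would be pointless if all SAEs counted. That is probably what was intended, but nothing in the SAP says so. The separate SAE total in 8.2.1 counts events, so it does not settle which participants are counted.

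It can also be said that little turns on the difference. SAP 3.1.2 sets no hypothesis or power for the primary endpoint, and SAP 10.1 sets no termination criteria. Protocol 9.4.4 already plans incidence for SAEs and for related events ("device and/or procedure related events (e.g., possibly, probably or definitely related) will be calculated from time of treatment"), and SAP 8.2.2 promises a listing by participant of all SAEs, SADEs and ADEs. This stands: the related count is recoverable and the over-count errs on the cautious side. What remains open is which count is the primary result.

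The argument from the inferior meatus objective has limited force. Every participant is treated at both locations, and relatedness is graded to device and procedure, not to site. The corrected count removes unrelated events but does not isolate the inferior meatus.

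The probability range is too wide to support any weight, and N is not firm: the protocol enrols up to 30 and allows replacement. The defect in the text depends on neither. The case in SAP 8.2.2 is weaker, because its heading keeps the limit and the protocol is itself unsettled on whether all AEs or only listed types are collected (8.4 against 8.4.1 and 8.4.6).

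**Conclusion.** The concern holds. The primary endpoint has two conflicting definitions in current SAP text, and the one attached to the analysis, read as written, is all-cause SAE incidence. Each participant with only unrelated SAEs adds 1/30, or 3.3 percentage points, to the primary result. The 26% chance of at least one unrelated SAE assumes a 1% rate carried over from a study of middle meatus treatment alone, and it ranges from 0.8% to 81% over the uncertainty in that rate. Type I error, power and sample size are unaffected. It should be fixed because it concerns the primary endpoint and the correction is close to free.

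**What to change.** Reword the rule in SAP 8.2.1 so that the primary endpoint is the number and percentage of safety-population participants with at least one SAE adjudicated as related to the procedure and/or the device. Deleting the SAE term from the present sentence, or putting procedure-related in front of it, gives the same count; the full wording also fixes the population and the percentage.

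Make the parallel change in SAP 8.2.2 so that the rule matches its heading. Keep all-cause SAE and AE incidence as supportive summaries, as Protocol 9.4.4 already plans.

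Two optional additions could go in with the same edit: an exact 95% CI for the primary proportion, and one term for the third relatedness grade, which is called possibly related in SAP 8.2.1, SAP 8.2.2 and Protocol 9.4.4 but potentially related in the grading scale of Protocol 8.4.5.2.

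The cost is two sentences of SAP wording. No new data are needed, since relatedness is adjudicated for every AE, and no tables beyond those already planned.
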